We will use dual energy x-ray absorptiometry (DXA) scans to measure BMD annually at 3 anatomical sites (lumbar spine, total hip, and wrist). Additionally, we will derive the trabecular bone score (TBS), an index of lumbar spine trabecular microarchitecture.

Hypothesis: Relative to women using DMPA only (without tenofovir exposure) and women using PrEP only (without DMPA exposure), women concurrently using TDF-based PrEP and DMPA will have lower bone mass and more disruptions in bone microarchitecture.

2. We will investigate whether young women concurrently using TDF-based PrEP and DMPA experience: 1) higher rates of bone turnover, a direct precursor to bone loss and 2) subclinical kidney injury and hypoestrogenism, markers of two mechanistic pathways between TDF and DMPA use and bone mass

At baseline, 3, 6, 12, and 24 months, we will measure:

- 1) Markers of bone formation and resorption (e.g. NTX, P1NP, serum intact parathyroid hormone, total and bioavailable 25-OH-vitamin D)
- 2) Markers of kidney function (phosphate, glucose, creatinine, total protein, albumin) and
- 3) Markers of estrogen (serum estradiol, sex hormone binding protein, and the occurrence of amenorrhea)

Hypothesis: Relative to women using DMPA only and PrEP only, women concurrently using TDF-based PrEP and DMPA will have increased bone turnover markers and PTH. In addition, women concurrently using TDF-based PrEP and DMPA will have more frequent subclinical kidney injury (relative to women without tenofovir exposure) and reduced serum estrogen (relative to women without DMPA exposure).

3. Using mediation analysis, we will identify the degree to which the pathways through subclinical kidney injury and hypoestrogenism account for changes in bone density among women concurrently using TDF-based PrEP and DMPA

We will conduct mediation analysis to determine the degree to which changes in the pathways through subclinical kidney injury, hypoestrogenism and the combination of these pathways account for changes in bone density.

Hypothesis: The pathway through hypoestrogenism will be a stronger link between concurrent TDF-based PrEP and DMPA use and bone density changes.

Population

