The primary analysis will be separate comparisons of the annualized rates of change in BMD and TBS of the spine and hip between women using PrEP and DMPA concurrently versus women using DMPA only (comparison 1), women using PrEP only (comparison 2), and women using neither (comparison 3). Analyses will account for baseline BMD.

Aim 2, part 1. We will investigate whether young women concurrently using TDF-based PrEP and DMPA experience higher rates of bone turnover relative to women using either agent singly or neither agent

This outcome will be defined by the percent change from baseline of serum levels of NTX and P1NP over 24 months. Secondary outcomes will include: 1) percent change from baseline in serum levels of intact PTH, total 25-(OH)D, bioavailable (i.e. unbound or free) 25-(OH)D calculated from vitamin D binding protein (VDBP) using the standard equation.

$$\text{Free 25(OH)D} = \frac{\text{total 25(OH)D}}{1 + (6 \times 10^3 \times \text{albumin}) + (7 \times 10^8 \times \text{DBP})}$$

To test the hypothesis that combined PrEP and DMPA use is associated with greater bone turnover than DMPA use alone, we will use time-dependent linear mixed-effects regression models to compare mean percent changes in NTX and P1NP between concurrent users of PrEP and DMPA versus users of DMPA only. Secondary powered comparisons will be between: a) concurrent users of PrEP and DMPA versus users of PrEP only; b) users of PrEP only versus users of condoms only; c) users of DMPA only vs users of condoms only. Analysis of the percent change from baseline in serum levels of intact PTH, total 25-OH-D and bioavailable 25-OH-D over 24 months will follow a similar approach. All analyses will be adjusted for confounders and we will consider a broad range of demographic, medical, lifestyle, and sexual behavior characteristics as potential confounders.

Aim 2, part 2. We will investigate whether young women concurrently using TDF-based PrEP and DMPA experience elevated markers of subclinical kidney injury relative to women using TDF-based PrEP alone

This outcome will be defined as having either:

- 1) eGFR decline ($\geq 25\%$ decline from baseline or creatinine clearance $< 60 \text{ mL/min}$). GFR will be calculated using the Chronic Kidney Disease Epidemiology (CKDE) collaboration equation

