- 2) proximal tubular injury (tubular proteinuria defined as elevated urine protein with urine albumin-protein ratio < 0.4 , euglycemic glycosuria, phosphaturia defined as increased urinary excretion of phosphorus $> 15\%$ or maximum rate of tubular phosphate reabsorption to the glomerular filtration rate).

These markers were selected because they are routinely available in clinical practice and have been used in prior studies. The cutoff of $\geq 25\%$ for eGFR decline was adapted from established criteria for the diagnosis of acute kidney injury;⁴¹ eGFR decline of this magnitude has been associated with increased morbidity and mortality.²²⁻²⁴

To determine whether young women using PrEP alone or concurrently with DMPA experience higher rates of subclinical kidney injury, we will perform a qualitative comparison of the incidence of individual markers of kidney injury among women using PrEP (alone or concurrently with DMPA) versus women who have no exposure to TDF.

Aim 2, part 3. We will investigate whether young women concurrently using TDF-based PrEP and DMPA experience elevated markers of hypoestrogenism relative to women using DMPA alone

This outcome will be defined as the percent change from baseline serum estradiol over 24 months and we will adjust for sex hormone-binding protein.⁵⁶ The secondary outcome will be based on self-reported missed menses, with > 3 missed menses in a row categorized as amenorrhea.

To determine whether young women concurrently using DMPA alone or concurrently with PrEP experience greater frequency of hypoestrogenism, we will conduct time-dependent logistic

regression among women using DMPA and women not exposed to DMPA, comparing the proportion of visits with hypoestrogenism.

Aim 3. Using mediation analysis, we will identify the degree to which the pathways through subclinical kidney injury and hypoestrogenism account for changes in bone density among women concurrently using TDF-based PrEP and DMPA

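### Aim 2 part 2 sets out to determine whether PrEP users have higher rates of kidney injury, but fixes a qualitative comparison that can neither separate an excess from chance nor bound it

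*Protocol*

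**What the plan says.** The hypothesis under Aim 2 (Study Methods, Aims) is directional: "women concurrently using TDF-based PrEP and DMPA will have more frequent subclinical kidney injury (relative to women without tenofovir exposure").

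The Data Analysis section, Aim 2 part 2, states its purpose as: "To determine whether young women using PrEP alone or concurrently with DMPA experience higher rates of subclinical kidney injury". The method follows in the same sentence: "we will perform a qualitative comparison of the incidence of individual markers of kidney injury among women using PrEP (alone or concurrently with DMPA) versus". The comparator is the group without TDF exposure.

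The outcome is introduced with "This outcome will be defined as having either" of two components. The first is "1) eGFR decline". The second is proximal tubular injury, made up of tubular proteinuria, euglycemic glycosuria and phosphaturia. That gives four markers. Table 5 ranks them: eGFR decline is in the primary column and the tubular markers are in the secondary column.

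The neighbouring analyses are model-based. Part 1 uses linear mixed-effects models, part 3 uses logistic regression, and Aim 3 uses regression with bootstrapped standard errors. The last sentence of part 1 reads: "All analyses will be adjusted for confounders and we will consider a broad range of demographic, medical, lifestyle, and sexual behavior characteristics as potential confounders".

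**The concern.** The stated purpose is to decide a question, but the stated method only places incidences side by side. With no interval, test or margin, two different incidences cannot be called different beyond chance, and two similar incidences cannot be called similar within any limit. PrEP is offered to everyone and taken up by choice, so an unadjusted comparison also mixes the effect of TDF with whatever leads women to accept it, and with any imbalance in DMPA use.

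This is not silence that a statistical analysis plan would fill. The protocol names the method, and a later plan that added a model and intervals would have to depart from that sentence. Kidney injury is among the study's safety questions, so a reader needs to be able to tell an absence of excess from a shortage of events.

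**Working it through.** The protocol gives no sample size, incidence, alpha or power for the kidney comparison, so there is no figure on this point to reproduce. As a check on the method, its BMD power figures do reproduce. A two-sided 0.05 normal approximation gives 91.0% for 225 vs 75 women, difference 2.2, SD 5 (stated 91%), and 73.8% to 90.1% for 270 vs 30, difference 2.5, SD 5 to 4 (stated 74-90%).

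**Inputs**
- From the sample size section: 500 women; 75% PrEP uptake among DMPA users.
- Assumed: the same uptake in condom users, so 0.75 × 500 = 375 exposed and 125 unexposed; complete follow-up; fixed exposure.
- Assumed: incidence p of 2%, 5% or 10% in the unexposed.

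**How precise would the comparison be?** With equal incidence p, the half-width is 1.96 × √[p(1−p)(1/375 + 1/125)].

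**What would a formal test detect?** For a true doubling, power is Φ{p / √[2p(1−2p)/375 + p(1−p)/125] − 1.96}.

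| p | Half-width (points) | Excess if doubled (points) | Power for doubling |
|---|---|---|---|
| 2% | 1.96 × √(0.0196 × 0.010667) = 2.8 | 2 | Φ(0.02/0.0161 − 1.96) = 24% |
| 5% | 1.96 × √(0.0475 × 0.010667) = 4.4 | 5 | Φ(0.05/0.0249 − 1.96) = 52% |
| 10% | 1.96 × √(0.09 × 0.010667) = 6.1 | 10 | Φ(0.10/0.0339 − 1.96) = 84% |

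These powers use the unpooled standard error. With the pooled null variance, Φ{(p − 1.96 s₀)/SE}, where s₀ = √[p̄(1−p̄)(1/375 + 1/125)], p̄ = (375 × 2p + 125 × p)/500 and SE is the denominator used above, they are 14%, 39% and 75%.

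The middle columns show where similar-looking rates mislead. At 2%, equal observed rates leave a doubling inside the interval (2.8 > 2). At 5%, exactly equal rates just exclude it (4.4 < 5), but an observed excess of about 0.6 points (5 − 4.4) brings it back. At 10%, equal rates exclude it. The planned comparison reports no interval, so a reader cannot tell which case applies.

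Uptake matters too. The same half-width formula gives 2.5, 3.8 and 5.3 points for 250 vs 250 (50% uptake), and 4.1, 6.4 and 8.8 points for 450 vs 50 (90% uptake).

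**How often would PrEP users look worse by chance?** This is a conditional illustration, because the protocol sets no rule for reading the incidences. With no true effect and 375 vs 125 women, exact binomial calculation gives:
- eGFR decline alone numerically higher in PrEP users: about 49% at incidences of 0.5% or more.
- At least one of four independent markers higher: with q ≈ 0.49 per marker, 1 − (1 − q)⁴ = 1 − 0.51⁴ = 93%.
- At least one of four, with person-level latent correlation 0.3 to 0.6 (simulated): 87-92%.
- At least one of four, with correlation 0.5 to 0.9 between the marker differences: 80% down to 63%.
- At least one of four, independent, at incidences of 0.1% to 0.2%: 73-88% (54-71% for 250 vs 250).
- At least three of four higher: 29-30%.

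**The case against.** The strongest reply is that descriptive reporting suits rare events. Table 2 cites a mean net eGFR decline in women of only 1.47 to 1.73 mL/min, against a 25% threshold, so the primary marker may be rare. The power calculation is based on Aim 1, and at 2% incidence 500 women yield about 10 events (500 × 0.02), so a formal test would settle little. This stands as a case for modest claims. It does not rescue a sentence whose aim is to determine whether rates are higher, and few events make intervals more useful, not less.

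Four stronger readings are tempting, and the documents do not support them.
- A reader might infer that the plan would signal kidney harm about nine times in ten under no effect. No passage says that an excess on any one marker means harm. Table 5 ranks eGFR decline first and the outcome is an either/or composite.
- A reader might infer a contradiction with the promise to adjust all analyses. That sentence closes part 1, so whether it reaches part 2 is open. If it does, the qualitative comparison conflicts with it; if not, a self-selected exposure goes unadjusted.
- A reader might infer that renal safety will be claimed from similar incidences. No passage plans such a claim.
- A reader might infer that Aim 3 inherits the weakness. It fits its own models and does not use the part 2 comparison. Clinical kidney monitoring and the monitoring committee's reviews are also separate.

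**Conclusion.** The point holds as a mismatch between purpose and method. Part 2 asks whether PrEP users have higher rates of kidney injury and commits to a comparison that cannot answer, because it provides no measure of uncertainty and no adjustment. Of the three Aim 2 parts, it alone lacks an inferential method.

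Under the assumed 375 vs 125 split, the unreported uncertainty is about ±2.8 to ±6.1 percentage points for incidences of 2% to 10%. A doubling could pass unnoticed at 2%, and quite easily at 5%. These sizes rest on assumed incidences and on equal uptake in both contraceptive groups. The mismatch itself rests on the protocol's wording alone. The chance of PrEP users merely looking worse runs from about one half to above nine in ten depending on how the incidences are read, and lower if events are very rare. It illustrates the open reading and is not an error rate of the plan. The matter should be corrected, but it does not touch the primary BMD analysis.

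**What to change.** In Data Analysis, Aim 2 part 2, replace the qualitative comparison with text such as:

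> For each kidney marker we will estimate the incidence in each group, and the risk difference and risk ratio with 95% confidence intervals, from a regression model that yields these measures (for example modified Poisson with robust per-woman variance, with standardisation for the risk difference). Models will be adjusted for DMPA use and a small prespecified set of confounders. When events are few, exact or penalised methods and unadjusted intervals will be used. eGFR decline is the lead outcome and the tubular markers are supportive. Higher rates will be concluded only if the interval for the lead outcome excludes no difference. Otherwise the upper bound will be reported and no claim of renal safety made.

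The confounder set must be small, because a handful of events cannot carry the broad list contemplated in part 1. If the sponsor prefers a descriptive analysis, the purpose should be restated as descriptive and the intervals still reported.

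Two points in the same section need reconciling first. The heading compares concurrent users with users of PrEP alone, while the analysis compares any PrEP use with no TDF. The outcome is an either/or composite in the text, while Table 5 splits it into primary and secondary definitions.

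The cost is a wording change and a little more analysis of samples and data already planned, with no added participants or procedures. Intervals for rare markers will be wide, so the conclusion may be more cautious.

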Subclinical kidney injury	
 Urine: phosphate, glucose, creatinine, total protein, albumin Serum: phosphate, glucose, creatinine 	eGFR decline calculated using Chronic Kidney Disease Epidemiology equation ($\geq 25\%$ decline from baseline or creatinine clearance $<60 \text{ mL/min}$)	
 Tubular proteinuria: elevated urine protein with urine albumin: protein ratio <0.4, Euglycemic glycosuria, Phosphaturia defined as increased fractional excretion of phosphorus $>15\%$ or maximum rate of tubular phosphate reabsorption to the glomerular filtration rate
Hypoestrogenism	
 Serum estradiol Sex hormone-binding globulin 	Percent change from baseline of serum estradiol with	Frequency of amenorrhea, defined as the absence of menses for at least 3 menstrual cycles

Retention and study exit

Upon completion of study follow up, women will be provided with referrals to clinics of their choice to continue contraceptive and PrEP provision. Since the interim guidelines for HIV prevention now include PrEP, by the time this study is completed, we anticipate that PrEP will be available through public facilities. We will provide participants with information about which facilities are actively providing PrEP and link them to services at that clinic via a referral.

Special circumstances

a. HIV seroconversion

HIV rapid testing will be conducted quarterly during follow up. We expect the rate of HIV seroconversion to be very low, due to the use of PrEP and repeated counseling about HIV prevention and PrEP. However, in the event of HIV positive rapid test results, PrEP will be stopped immediately and additional blood samples will be drawn for confirmatory EIA testing, plasma HIV RNA quantification, drug resistance, and/or drug levels. When with confirmed HIV seroconversion will be extensively counseled and referred to local clinics providing antiretroviral medications and HIV care. At the visit when HIV seroconversion is confirmed, women will be exited from the study once the set of study procedures for an exit visit are completed. HIV seroconverters who are pregnant will be referred for services to prevent mother to child HIV transmission and study staff will go to great lengths to ensure that women experience no delays in accessing these services.

b. Pregnancy

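### Aim 2 parts 2 and 3 ask whether concurrent use is worse than one agent alone, but the stated analyses use only agent-unexposed women as reference, and the primary estradiol outcome has no matching model

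*Protocol*

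**What the plan says.** The protocol frames the kidney and estrogen questions in three ways.

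- **Section V headings.** Part 2 asks whether concurrent users "experience elevated markers of subclinical kidney injury relative to women using TDF-based PrEP alone". Part 3 asks whether they "experience elevated markers of hypoestrogenism relative to women using DMPA alone".
- **Aim 2 hypothesis (Section III, Aims).** Concurrent users are expected to have "more frequent subclinical kidney injury (relative to women without tenofovir exposure) and reduced serum estrogen (relative to women without DMPA exposure".
- **Section V analyses.** Part 2 is a qualitative comparison of marker incidence "among women using PrEP (alone or concurrently with DMPA) versus women who have no exposure to TDF". Part 3 is a time-dependent logistic "regression among women using DMPA and women not exposed to DMPA, comparing the proportion of visits with hypoestrogenism".

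On the estrogen outcome, part 3 states: "This outcome will be defined as the percent change from baseline serum estradiol over 24 months". Table 5 gives the same primary measure, "Percent change from baseline of serum estradiol", although that cell breaks off in the text available. The secondary outcome is amenorrhea. Table 5 counts three or more cycles without menses, while Section V requires more than three missed in a row.

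Part 1 of the same aim is more explicit. It uses linear mixed-effects models on percent change, compares concurrent users with DMPA-only users, and lists "concurrent users of PrEP and DMPA versus users of PrEP only" among its secondary comparisons.

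**The concern.** In each heading the single-agent group is the reference. In the matching analysis that group sits on the exposed side with the concurrent users, and the reference is women unexposed to the agent. The contrast posed in the heading is therefore not among the stated analyses. The hypothesis in Section III supports the unexposed reference groups, but it puts only concurrent users on the exposed side, so it does not match the analyses either.

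This matters because the summary of joint effects in Section II leaves open whether one agent acts through the other's pathway. Two contrasts bear on that: whether adding DMPA worsens kidney markers in PrEP users, and whether adding PrEP lowers estradiol further in DMPA users. Those are the two that are missing. A clear DMPA effect on estrogen could be misread as an answer to the part 3 heading even if PrEP did nothing.

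Separately, the outcome named as primary for estrogen is continuous, but the only model is for a binary state called hypoestrogenism. The text gives no estradiol cut-off that defines that state.

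**Working it through.** **Passages side by side**

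| | Heading (Section V) | Hypothesis (Section III) | Analysis (Section V) |
|---|---|---|---|
| Kidney | concurrent vs PrEP only | concurrent vs no TDF | all PrEP users vs no TDF |
| Estrogen | concurrent vs DMPA only | concurrent vs no DMPA | all DMPA users vs no DMPA |

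No two columns agree in full. Hypothesis and analysis share a reference group but differ on who is exposed.

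**Inputs.** Section III, Sample size and study power, gives 300 DMPA and 200 condom users and, at 75% PrEP uptake, 225 concurrent and 75 DMPA-only women. PrEP uptake among condom users is not given. I assume 75% for illustration (150 PrEP only, 50 neither), with a range of 50–90%.

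**The plan's own figure.** No power is stated for parts 2 and 3. The nearest figure is the 91% in Table 4 for BMD: difference 2.2%, SD 5%, 225 vs 75.
- SE = 5 × √(1/225 + 1/75) = 5 × 0.1333 = 0.667.
- Power = Φ(2.2/0.667 − 1.96) = Φ(1.34) = 0.91. It reproduces.

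**What the analyses estimate.** Let T be the TDF effect, D the DMPA effect and I their interaction. Group means relative to neither agent are: concurrent T + D + I, PrEP only T, DMPA only D. Groups are taken as merged, with no term for the other agent.
- Part 2 as written, 375 vs 125: [225(T + D + I) + 150T]/375 − 75D/125 = (T + 0.6D + 0.6I) − 0.6D = **T + 0.6I**. The heading asks for (T + D + I) − T = **D + I**.
- Part 3 as written, 300 vs 200: [225(T + D + I) + 75D]/300 − 150T/200 = (D + 0.75T + 0.75I) − 0.75T = **D + 0.75I**. The heading asks for (T + D + I) − D = **T + I**.

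If DMPA lowers estradiol and PrEP has no effect (T = I = 0), part 3 shows the full D while the heading's contrast is zero. If DMPA adds to kidney injury without interaction, part 2 shows none of that addition. A concurrent-minus-DMPA-only difference d moves the combined DMPA mean by (225/300)d = 0.75d, and this cannot be told apart from the DMPA effect.

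**Precision of the direct estradiol contrast, in SD units.** SE = √(1/n₁ + 1/n₂); the difference detectable with 80% power is (1.96 + 0.842) × SE.
- 225/75: SE 0.133; 95% CI half-width 1.96 × 0.133 = 0.26; detectable 0.37.
- 150/150: SE 0.1155; detectable 0.32.
- 270/30: SE 0.1925; detectable 0.54.

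**Precision of the direct kidney contrast.** Half-width = 1.96 × √[p(1 − p)(1/225 + 1/n₂)], with n₂ PrEP-only women and incidence p both assumed. Results in percentage points:

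| n₂ (uptake) | p = 2% | p = 5% | p = 10% |
|---|---|---|---|
| 100 (50%) | 3.3 | 5.1 | 7.1 |
| 150 (75%) | 2.9 | 4.5 | 6.2 |
| 180 (90%) | 2.7 | 4.3 | 5.9 |

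Attrition, method switching and confounder adjustment are ignored, so real precision is likely lower. Repeated measures could raise it for estradiol.

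**The case against.** The strongest reply is that the headings are the outliers. The hypothesis in Section III uses the unexposed reference groups, and the sentences introducing the two analyses match the analyses. Headings here are loose in general: part 1's heading also mentions women using neither agent, yet no concurrent-versus-neither comparison follows. On that view, rewording two headings is enough. This stands in part. It would remove one contradiction, but the analyses would still not isolate concurrent users as the hypothesis does, and the cross-pathway question would remain unanswered.

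The kidney text may also intend PrEP-only and concurrent users to be shown side by side, and the estrogen regression may include a PrEP term. Neither is stated. Side-by-side display would still leave women without TDF exposure as the reference. It is true that the T, D, I and 0.75d results hold only if the groups are merged with no such term.

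An SAP, which is not at hand, could supply an estradiol cut-off or added contrasts. That would fill in detail. It would not remove the conflict between the protocol's own question and its own analysis, or between its continuous primary outcome and its logistic model. The break in the Table 5 cell does not matter, because part 3 states the outcome in full.

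Two limits on the numbers stand. The protocol gives no estradiol SD or relevant difference, so 0.37 SD cannot be judged clinically. At 2% incidence only about 4.5 events (225 × 0.02) and 2 to 3.6 events (100 to 180 × 0.02) are expected, too few for the normal approximation to be reliable.

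**Conclusion.** The plan is wrong as written on this point and should be corrected. Followed exactly, parts 2 and 3 give the overall TDF effect on kidney markers and the overall DMPA effect on estrogen. Both are useful, but neither answers its heading. The percent change in estradiol, named as the primary estrogen outcome, has no stated analysis, and amenorrhea has two definitions that differ for a woman who misses exactly three cycles.

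These conclusions rest on the text alone. The figures only show what the missing contrasts could deliver. The estradiol figures use the protocol's group sizes; the kidney figures rest on assumed uptake and incidence. Aim 1, Aim 2 part 1 and the Aim 3 models are not invalidated.

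**What to change.** - Reconcile the Aim 2 hypothesis in Section III with the headings and analyses of parts 2 and 3 in Section V, and state the main contrast for each part.
- Report the four exposure groups separately.
- **Kidney:** add concurrent versus PrEP only as an estimate with a 95% CI, descriptive if events are few. Keep TDF versus no TDF.
- **Estrogen:** analyse percent (or log) change in estradiol with the linear mixed model already stated in part 1. Add concurrent versus DMPA only, and keep DMPA versus no DMPA.
- Use logistic regression for amenorrhea, with one definition in Table 5 and Section V.

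If the single-agent contrasts are not wanted, the headings should be reworded to match the hypothesis, the exposed group limited to concurrent users, and the protocol should say that these parts do not address cross-pathway effects.

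The cost is wording changes in Section III (Aims and Table 5) and Section V, plus a little extra analysis of data the study already collects. The downside is modest precision for the direct contrasts, especially for kidney markers, and for estradiol if PrEP uptake approaches 90%.
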